6.6 Assessment of PrEP use

The use of oral FTC/TDF as PrEP (either off-study or provided in the study) may impact study outcomes (e.g., by lowering HIV-1 incidence with a loss of study power). Dried blood spot (DBS) samples will be collected and stored for assessment of quantitative concentrations of intracellular tenofovir diphosphate (TFV-DP) (see Section 11.9). DBS samples will be collected and stored at pre-specified DBS sample collection days, which may vary by study site. The calendar-based selection of sample collection days will ensure representative sampling of participants across the entire visit schedule at all sites throughout the study. A detailed DBS sampling plan, specified in the statistical analysis plan, will be developed to prospectively monitor FTC/TDF use during the trial to inform the DSMB and to assess the potential impact of FTC/TDF use on endpoint accrual during the study. Prevalence of oral PrEP use will be reported both as the estimated percentage of person-years at-risk during highly adherent PrEP use (above the concentration of TFV-DP designated as consistent with daily dosing) and the estimated percentage of personyears at-risk during any detectable PrEP use (concentration of TFV-DP above the lower limit of detection for the DBS assay). PrEP use measures will be reported by arm to the DSMB in the closed session; in addition both the OG and the protocol team leadership will see pooled estimates of FTC/TDF use.

6.7 Randomization of treatment assignments

The randomization sequence will be obtained by computer-generated random numbers through an Interactive Web Response System (IWRS) under provision by the sponsor and provided to each HVTN CRS. The randomization will be stratified by HVTN CRS and done in blocks to ensure balance across arms. At each institution, the pharmacist with primary responsibility for dispensing study products is charged with maintaining security of the treatment assignments. Participants and site staff will be blinded as to the treatment group assignment throughout both Stage 1 and Stage 2, if it occurs.

6.8 Blinding

The study participants, study-site personnel (except for those with primary responsibility for study vaccine preparation and dispensing), and investigators will be blinded to study vaccine allocation throughout the study (both Stage 1 and Stage 2, if it occurs).

Study product assignments are accessible to those HVTN CRS pharmacists and contract monitors, and SDMC staff who are required to know this information in order to ensure proper trial conduct. Any discussion of study product assignment between pharmacy staff and any other HVTN CRS staff is prohibited. The DSMB members also are unblinded to treatment assignment in order to conduct review of trial safety and efficacy.

When a participant leaves the trial prior to study completion, the participant will be told she must wait until all participants have completed follow-up to learn her treatment assignment.

Emergency individual unblinding decisions will be made by the site investigator when the timing is critical for medical management. Otherwise, the HVTN 705/HPX2008 PSRT should be consulted before emergency unblinding occurs.

6.9 Statistical analysis

Statistical analysis will be done by close collaboration between HVTN SDMC and Janssen Vaccines. A general description of the statistical methods to be used to analyze the efficacy, safety and immunogenicity data is outlined below. Specific details will be provided in the SAP.

This section describes the final study analysis with unblinded treatment groups. The primary efficacy analysis will be performed when all participants have reached the Month 24 visit or discontinued earlier. The primary analyses of safety will be performed on the FAS. The primary analysis of vaccine efficacy will be based on the PP population. Secondary analyses of vaccine efficacy will be based on the MITT population and the FIS. Analyses of vaccine immunogenicity and immune correlates of risk will be based on the IC-at risk, IC-PP and the FIS. In general vaccination assignment will follow the as treated principle, except for analyses using the MITT population.

Analyses for primary endpoints will be performed using SAS and R.

No multiplicity corrections will be used unless stated otherwise.

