5.2 Secondary objectives and endpoints

Secondary objective 1:

To evaluate vaccine efficacy from enrollment through 24 months

Secondary endpoint 1:

HIV-1 infection diagnosed after enrollment through 24 months post enrollment

Secondary objective 2:

To evaluate vaccine efficacy from enrollment through the end of the study if Stage 2 occurs

Secondary endpoint 2:

HIV-1 infection diagnosed after enrollment through the end of the study

Secondary objective 3:

To evaluate vaccine efficacy from month 12 through month 24

Secondary endpoint 3:

HIV-1 infection diagnosed after month 12 through 24 months post enrollment

Secondary objective 4:

To evaluate vaccine efficacy from month 12 through the end of the study if Stage 2 occurs

Secondary endpoint 4:

HIV-1 infection diagnosed after month 12 through the end of the study post enrollment

Secondary objective 5:

To evaluate the immunogenicity of the vaccine regimen

Secondary endpoint 5:

Immune responses at the study visits following the third and fourth vaccinations from assays based on the HVTN Laboratory Assay Algorithm such as vaccine-specific binding antibodies and T-cell responses.

Secondary objective 6:

To evaluate immunogenicity and immune response biomarkers among vaccine recipients after the third vaccination as correlates of risk of subsequent HIV acquisition and correlates of vaccine efficacy, if deemed applicable.

Secondary endpoint 6:

Immune responses from assays based on the HVTN Laboratory Assay Algorithm (available at https://atlas.scharp.org/) and/or more assays down-selected from a larger pool of pilot studies, in HIV-1-infected vaccine cases and HIV-1-uninfected vaccine controls

Secondary objective 7:

To evaluate VE adjusting for various demographic and other baseline characteristics

Secondary endpoint 7:

HIV-1 infection diagnosed after the third vaccination by demographic and other baseline characteristics

Secondary objective 8:

If significant positive evidence of vaccine efficacy from month 7 through 24 months is seen, to assess if and how vaccine efficacy depends on genotypic characteristics of HIV such as signature mutations

Secondary endpoint 8:

HIV-1 infection diagnosed after month 7 through Month 24 and genotypic characteristics of viral sequences from HIV-1—infected participants at HIV-1 diagnosis, such as signature site mutations

Secondary objective 9:

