To evaluate and compare genomic sequences of viral isolates from HIV-1-infected vaccine and placebo recipients, and use sieve analysis methods to assess whether VE differs by genotypic or phenotypic characteristics of exposing HIVs and whether there is evidence of vaccine-induced immune pressure on the viral sequences

Secondary endpoint 9:

Viral sequences from HIV-1—infected participants at the earliest available postinfection timepoint and possible subsequent visits

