6.3 Primary analysis of vaccine efficacy

We define the vaccine efficacy parameter, VE(7-24), for the primary analysis as 1 minus the cumulative incidence ratio (vaccine/placebo) of the HIV-1 endpoint between Month 7 and Month 24 after enrollment in the PP population.

The cumulative incidence parameters used to define VE(7-24) will be estimated using the transformed Nelson-Aalen estimator for the cumulative hazard function at Month 24 in the PP population.

The target parameter for the primary analysis of VE is VE(7-24). A two-sided 95% log-cumulative-hazard based Wald confidence interval will be reported for VE(7-24), without adjustment for interim monitoring.

The primary analysis also reports a test of the null hypothesis

H0: VE(7-24) = 0% against the alternative hypothesis H1: $VE(7-24) \neq 0\%$

using a 2-sided α =0.05 level Wald test of the equality of log cumulative hazard functions at Month 24 in the PP population for the vaccine group and the placebo group. The p-value of this test will also be reported, where this p-value will not be adjusted for interim monitoring.

6.3.1 Analysis to determine whether or not the trial will advance into Stage 2

If the lower bound of the 2-sided 95% confidence interval for VE(7-24) is > 0% (equivalently, the 1-sided p-value for testing H0: VE(7-24) $\le 0\%$ vs. H1: VE(7-24)>0% is below 0.025), trial participants will continue blinded follow-up through the end of the study (timepoint of final analysis). On the other hand, if the lower bound of the 95% confidence interval for VE(7-24) is $\le 0\%$, Stage 2 will not occur and the trial participants will be unblinded at the end of Stage 1 (timepoint of primary/final analysis). Pending availability and outcome of primary analysis results, participants will continue their normal scheduled visits beyond Month 24.

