6.9.5.3 Secondary vaccine efficacy and activity analyses of viral sequences

Vaccine efficacy and genotypic characteristics

A variety of methods may be used to assess genotypic characteristics of HIV as potential effect modifiers of VE(0-24) [52]. The TMLE for estimating cumulative incidences in the presence of competing risks will also be applied as described in Benkeser et al. (2016, PhD dissertation). Like the TMLE efficacy analysis, this analysis incorporates Super Learner to increase precision. Details can be found in the SAP.

Sieve analysis

Acquisition sieve analysis methods including genome scanning tests described in Gilbert et al. and their extensions will be used to evaluate the relationship between VE(7-24) and VE(0-24), and the genotypic differences between the incoming exposing/founder sequences and the HIV insert sequence(s) represented in the vaccine construct [53].

7 Selection and withdrawal of participants

Participants will be healthy, HIV-uninfected (seronegative) women who comprehend the purpose of the study and have provided informed consent. Volunteers will be recruited and screened; those determined to be eligible, based on the inclusion and exclusion criteria, will be enrolled in the study. Final eligibility determination will depend on results of medical history, hemoglobin, physical examinations, and answers to self-administered and/or interview questions.

Investigators should always use good clinical judgment in considering a volunteer's overall fitness for trial participation. Some volunteers may not be appropriate for enrollment even if they meet all inclusion/exclusion criteria. Medical, psychiatric, occupational, limited ability to communicate, or other conditions may make evaluation of safety and/or immunogenicity difficult, and some volunteers may be poor candidates for retention.

Determination of eligibility, taking into account all inclusion and exclusion criteria, must be made within 45 days prior to enrollment unless otherwise noted in Sections 7.1 and 7.2.

The HVTN 705/HPX2008 PSRT will be consulted for questions related to selection and withdrawal of participants that are not specifically addressed below or are ambiguous. All attempts to achieve consensus will be made. In the event that consensus cannot be reached, the participant will not be enrolled.

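### No error-rate rule is stated for the genome scan of secondary objective 9, so the protocol's default of no multiplicity correction reaches it

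*Protocol*

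**What the plan says.** Protocol 6.9 gives the rule for all analyses under it: "No multiplicity corrections will be used unless stated otherwise".

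Protocol 6.9.5.3 falls under that rule and covers two kinds of sequence analysis.

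- For the sieve analysis it names "Acquisition sieve analysis methods including genome scanning tests", by reference to a published method and unspecified extensions of it. These are applied to both VE(7-24) and VE(0-24), against the insert sequence or sequences. This serves secondary objective 9 (protocol 5.2), which is to "use sieve analysis methods to assess whether VE differs by genotypic or phenotypic characteristics of exposing HIVs" and to look for vaccine-induced immune pressure. The objective carries no precondition.
- For genotypic effect modification it says "A variety of methods may be used to assess genotypic characteristics of HIV as potential effect modifiers", and then "Details can be found in the SAP". This serves secondary objective 8, which does carry a precondition: "If significant positive evidence of vaccine efficacy from month 7 through 24 months is seen". Its targets are described only by example, "such as signature site mutations".

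The SAP repeats objectives 8 and 9 in its section 2.2. Its efficacy sections (8.1 to 8.5) and its list of end-of-Stage-1 analyses (section 9) contain no sieve or genotype analysis. Section 8.2.4 concerns only the number of founder viruses. No site list, per-site test, significance level or error-rate rule for the scan appears in either document.

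**The concern.** A default of no adjustment is defensible for one primary test with a short list of named secondary analyses. A scan is different in kind: it makes many vaccine-versus-placebo comparisons in one pass and then reports those that stand out. With no rule on the error rate across sites, a vaccine with no sieve effect can still yield sites that appear to differ between arms, and the reader cannot tell these from signal. The threshold could also be chosen after the sequences have been seen by arm.

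The documents do state multiplicity control where they intend it. SAP 10.1.1 sets a family-wise rate of 0.05 for harm monitoring, and SAP 8.1 and 8.2.2 plan simultaneous confidence intervals for efficacy over time. The protocol's account of the monkey challenge study (Table 4-8) reports a five-fold Bonferroni correction. The scan is likely to be a larger family than five comparisons, and nothing is stated for it.

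**Working it through.** **Inputs**

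- Number of sites m: not given; treated as unknown and shown over a range.
- Per-site level: not given for the sieve analysis. Two-sided 0.05 is assumed, by analogy with the 95% interval in protocol 6.3; 0.01 is also shown.
- Infections available: Table 6-5 medians for post-Month-7 infections, 128 at VE 0% and 97 at VE 50%. Protocol 11.8 makes sequencing optional, so there may be fewer sequences.

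**1. Reproducing the infection counts.** Use placebo incidence 0.042 and dropout 0.10 per year, 1,300 per arm, and VE halved in the first 7 months (protocol 6.4.1). Expected infections per arm in Months 7-24 are 1300 × exp(−(h₁+d)·7/12) × h₂/(h₂+d) × [1 − exp(−(h₂+d)·17/12)], where h₁ and h₂ are the infection rates before and after Month 7 and d is the dropout rate.

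- Placebo (h₁ = h₂ = 0.042): 64.5. At VE 0% the total is 129.0, against a stated median of 128.
- Vaccine at VE 50% (h₁ = 0.0315, h₂ = 0.021): 32.9. The total is 97.4, against a stated median of 97.

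The splits used below are 64:64 and, for 97 divided about 1:2, 32:65.

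**2. Independent sites.** P(at least one false positive) = 1 − (1 − α)^m.

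| Sites m | α = 0.05 | α = 0.01 |
|---|---|---|
| 10 | 40% | 10% |
| 50 | 92% | 39% |
| 59 | 95% | 45% |
| 100 | 99.4% | 63% |
| 500 | about 100% | 99% |

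At 0.01, 299 sites are needed to reach 95%.

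**3. Exact Fisher test per site.** This test is conservative, so its actual size replaces 0.05. Sites needed for 95% are ln(0.05)/ln(1 − size), rounded up.

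| Mismatch frequency | Size, 32:65 | Sites for 95% | Size, 64:64 | Sites for 95% |
|---|---|---|---|---|
| 2% | 0.0084 | 357 | 0.0010 | 2,973 |
| 5% | 0.0242 | 123 | 0.0118 | 253 |
| 10% | 0.0314 | 94 | 0.0233 | 128 |
| 20% | 0.0385 | 77 | 0.0297 | 100 |
| 30% | 0.0395 | 75 | 0.0308 | 96 |
| 50% | 0.0336 | 88 | 0.0298 | 99 |

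For 10-50% mismatch the range is 75 to 128 sites. Near-conserved sites add little.

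**4. Linked sites.** Simulated equicorrelated two-sided z-tests at 0.05 (20,000 runs) give the chance of at least one false positive:

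| m | Correlation 0.2 | 0.5 | 0.8 |
|---|---|---|---|
| 59 | 91% | 66% | 31% |
| 100 | 98% | 78% | 36% |
| 500 | about 100% | 99% | 51% |

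**5. Objective 8.** At true VE 0% and 4.2% incidence, the precondition is met in 2.06% of trials (Table 6-2) or 2.18% (Table 6-4). False sites there therefore matter mainly when efficacy is real but does not vary by virus.

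**6. With adjustment.** Bonferroni at 0.05/m keeps the family-wise error at 1 − (1 − 0.05/m)^m. For m = 100 that is 0.0488, with a per-site level of 0.0005.

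**The case against.** The strongest reply is that the scan is specified by citation. The published method and its extensions may contain their own error control, in which case the default in 6.9 would be superseded in practice. The documents neither confirm nor exclude this, so a reader who infers a decision to judge each site at an unadjusted 0.05 goes beyond the text. No per-site level or test is written.

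Three further points stand.

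- Site count, level and correlation are all unstated. Across the cases above, the chance of a false site runs from about 10% or less to about 100%. It is tempting to say that chance findings are almost certain, but the documents do not support that without a site count.
- Objectives 8 and 9 should not be treated alike, because objective 8 has its precondition.
- This is a secondary objective in a trial that describes itself as proof of concept, its wording is to assess rather than to conclude, and no decision rule rests on individual sites.

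The reply does not remove the gap. The plan has a general rule that points towards no correction, the exception has to be stated to apply, and it is not stated. If adjustment is already intended, one sentence closes the matter.

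**Conclusion.** The point holds as a defect in the stated rule. The default in 6.9 reaches the objective 9 scan, and neither document makes an exception. If the scan is run that way, about 59 independent sites at 0.05, or about 75 to 130 variable sites with Fisher tests, give a 95% chance of at least one false site. With 100 sites at strong correlation (0.8) the chance is still about 36%, well above 5%. These figures rest on an assumed site count and per-site level, and on the Table 6-5 medians being fully sequenced.

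A reader might infer more, and three readings should be resisted.

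- Harm monitoring is not the SAP's only multiplicity control, given its simultaneous intervals for efficacy over time.
- For objective 8, the concern is limited in practice to positive efficacy that is uniform across viruses.
- The immune markers of secondary objective 6 also fall under the default, but they are assessed only if deemed applicable and the documents give no number of markers to be tested, so no size can be attached and no finding is made there.

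The primary efficacy analysis is unaffected.

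**What to change.** Add an exception to protocol 6.9 and 6.9.5.3, and a short sieve section to the SAP, stating:

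- the proteins or sites to be scanned and the per-site test;
- a minimum-variability filter applied without reference to treatment arm. A site with at most five minority residues at a 64:64 split, or at most two at 32:65, cannot reach 0.05 by Fisher's test even if all of them fall in one arm, so dropping such sites loses nothing;
- a prespecified false-discovery-rate or family-wise adjustment for site-scanning and signature-site tests, with unadjusted p-values alongside;
- that statements of a sieve effect at individual sites rest on the adjusted values.

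If the cited method already controls the error rate, say so and name the rate. The threshold, such as q ≤ 0.20, is the sponsor's choice. The SAP history records a final analysis on 2 May 2022, so the amendment should also say whether sequences had been examined by arm when the rule was written.

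The cost is a few sentences and trivial computing. The downside is that fewer individual sites will be flagged. At the Bonferroni level of 0.0005 for 100 sites with a 32:65 split, six minority residues all in the vaccine arm (p = 0.0009) would not qualify, while seven (p = 0.0003) would. A false-discovery-rate rule is generally less strict.

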6.9.1 Analysis variables

The analysis variables consist of baseline participant characteristics, safety, efficacy, and immunogenicity.

6.9.2 Baseline comparability

Treatment arms will be compared for baseline participant characteristics using descriptive statistics.

6.9.3 Safety/tolerability analysis

All safety analyses will be tabulated by treatment group (active vaccine, placebo) and based on the FAS.

6.9.3.1 Reactogenicity

The number and percentage of participants experiencing each type of reactogenicity sign or symptom will be tabulated by severity and treatment group and the percentages displayed graphically by arm. For a given sign or symptom, each participant's reactogenicity will be counted once under the maximum severity for each injection visit. In addition, to the individual types of events, the maximum severity of local pain or tenderness, induration or erythema, and of systemic symptoms will be calculated. Kruskal-Wallis tests will be used to test for differences in severity between arms.

6.9.3.2 AEs and SAEs

AEs will be summarized using MedDRA System Organ Class and preferred terms. Tables will show by treatment group the number and percentage of participants experiencing an AE within a System Organ Class or within preferred term category by severity and by relationship to study product. For the calculations in these tables, a participant with multiple AEs within a category will be counted once under the maximum severity and by causal relationship to study product. Formal statistical testing comparing

arms is not planned since interpretation of differences must rely heavily upon clinical judgment. Parallel analyses will include all AEs and AEs leading to participant withdrawal or early discontinuation of study product(s).

A listing of SAEs reported to the Janssen Global Medical Safety Group will provide details of the events including severity, relationship to study product, time between onset and last vaccination, and number of vaccinations received.

6.9.3.3 Reasons for vaccination discontinuation and early study termination

The number and percentage of participants who discontinue vaccination and who terminate the study early will be tabulated by treatment arm and including the reason for discontinuation.

6.9.4 Immunogenicity analysis

Data from quantitative assays will be summarized (tabulated/graphically presented per timepoint available) by treatment group: N, geometric means and corresponding 95% CIs, percentage positive responses/responders (if available).

Data from qualitative (ie, positive or negative) assays will be summarized by tabulating the frequency of positive responses for each assay by group at each timepoint that an assessment is performed.

6.9.5 Vaccine efficacy analyses

6.9.5.1 Primary vaccine efficacy analysis: HIV-1 infection

The primary analysis will be done in the PP population where participants becoming HIV infected or dropping out before the visit after the third vaccination or not having received all of the first 3 vaccinations within the specified time window or having a major specified protocol deviation, will be excluded from the analysis. The date of HIV-1 diagnosis will be the draw date of the first sample that leads to a positive test result by the diagnostic algorithm described in Section 10.3. Dropouts will be censored at the time of their last HIV-1 negative test. To evaluate the primary vaccine efficacy endpoint, the ratio of cumulative incidences of HIV-1 infection between Months 7 and 24 (vaccine vs. placebo), estimated using the transformed Nelson-Aalen cumulative hazard function estimator and tested via a Wald test. Cox proportional hazards model will also be used for estimating VE(7-24), measured by 1 minus the hazard ratio (vaccine vs. placebo) and for score testing whether the VE(7-24) differs from 0%.

As a sensitivity analysis to the primary analysis of vaccine efficacy in the PP population, targeted minimum loss-based estimation (TMLE) is used to estimate of this vaccine efficacy parameter. In particular, TMLE is used to estimate the cumulative incidences of HIV-1 infection over time for each of the vaccine and placebo groups, through to the final timepoint Month 24. These estimates will then be contrasted to estimate the primary VE parameter VE(7-24), which adjusts for covariates. This analysis has the ability to correct for bias due to measured participant covariates that predict both per-protocol status and HIV-1 infection. Iterative mean-based TMLE is used for this analysis as described in Benkeser et al. (2016, PhD dissertation). As part of the implementation of the TMLE the Super Learner is used to generate initial estimates of the conditional censoring distribution and the iterated conditional means [48]. The Super Learner library includes both parametric and nonparametric learning algorithms that are specified in the

SAP; the SAP also specifies the input variables considered by the different learning algorithms. Each learning algorithm considers adjustment for baseline demographic covariates and the baseline behavioral risk score built via supervised learning.

In addition, to assess potential time-effects of vaccine efficacy, the Kaplan-Meier method will be used to plot the estimated cumulative incidence rates over time for the vaccine and placebo groups. This method will be used to estimate cumulative vaccine efficacy over time, defined as [(1-ratio(vaccine/placebo) of cumulative incidence by time t)*100%], with the method of Parzen, Wei and Ying applied to estimate pointwise and simultaneous 95% Cis [49].

